Appendix 6. Simplified Mortality Score for the Intensive Care Unit 14.6 (SMS-ICU)

In trial settings, the variables are measured in the 24-h period before randomisation; further details are presented in Appendix 2 and in [43].

SMS	-ICU
Aį	ge
≤ 39 years → 0	
40-59 ye	ears → 5
60-79 ye	ars → 10
≥ 80 yea	ars → 13
Lowest systolic blood pressure	
≤ 49 mr	nHg → 6
50-69 mi	mHg → 5
70-89 mi	mHg → 3
≥ 90 mm	nHg → 0
Acute surgical admission	
No → 3	Yes → 0
Hematologic	malignancy or
metastatic cancer	
No → 0	Yes → 7
Vasopressors/inotropes	
No → 0	Yes → 4
Respiratory support	
No → 0	Yes → 5
Renal replacement therapy	
No → 0	Yes → 4

Total score and predicted					
	90-day mortality risk				
0	3.3 %	22	40.1 %		
3	4.8 %	23	43.4 %		
4	5.5 %	24	46.7 %		
5	6.2 %	25	50.1 %		
6	7.1 %	26	53.5 %		
7	8.0 %	27	56.9 %		
8	9.1 %	28	60.2 %		
9	10.3 %	29	63.4 %		
10	11.6 %	30	66.4 %		
11	13.1 %	31	69.4 %		
12	14.7 %	32	72.2 %		
13	16.5 %	33	74.8 %		
14	18.4 %	34	77.3 %		
15	20.5 %	35	79.6 %		
16	22.8 %	36	81.7 %		
17	25.3 %	37	83.7 %		
18	28.0 %	38	85.4 %		
19	30.8 %	39	87.0 %		
20	33.8 %	41	89.8 %		
21	36.9 %	42	91.0 %		
Use the worst values recorded					
during the first 24 hours in the ICII					

during the first 24 hours in the ICU.

The CLASSIC trial protocol Page 62/82

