In any multiple imputation, we will use all relevant outcomes and the stratification variables (site and metastatic or hematologic cancer), SMS-ICU¹⁴ at baseline, site of infection at baseline, comorbidities at baseline (ischemic heart disease or heart failure, chronic hypertension or chronic RRT), use of corticosteroids at baseline, mechanical ventilation at baseline, highest p-creatinine 24 hours prior to randomisation, habitual p-creatinine, p-lactate at baseline, participant weight at baseline, and volume of IV fluids given prior to randomisation. Multiple imputation will be performed separately in the two intervention groups before pooling the full dataset, and the primary result of the trial will be based on these data. The unadjusted, non-imputed analysis will also be presented. If multiple imputation is used, we will also include a best-worst worst-best case scenario to assess the potential impact of any pattern of missingness including that data are 'missing not at random' (MNAR criterion). In the 'best-worst-case' scenario it is assumed that all participants lost to followup in the experimental group e.g. have survived; and that all patients with missing outcomes in the control group have not survived. Conversely, in the 'worst-best-case' scenario, it is assumed that all participants who were lost to follow up in the experimental group have had a harmful outcome; and that all those lost to follow-up in the control group have had a beneficial outcome. When continuous outcomes are used, a 'beneficial outcome' will be defined as the group mean plus two

standard deviations (SD) of the group mean or highest possible value whichever is smallest, and a 'harmful outcome' will be defined as the group mean minus two SD of the group mean or lowest possible value whichever is highest.

General analytical principles

The analyses will be done in the intention-to-treat (ITT) population defined as all randomised participants for whom there is consent for the use of data. The conclusion of the trial will be based on the ITT analysis.

The per-protocol population is defined as the ITT population except those having one or more major protocol violations.

Statistical analyses

Primary outcome

Four analyses will be performed for the primary outcome:

Primary analysis:

1. Logistic regression analysis adjusted for the stratification variables¹⁵ (site and hematologic malignancy /metastatic cancer) in the ITT population. P-values will be two-tailed

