Sensitivity analyses:

A two-tailed logistic regression analysis adjusted for the stratification variables, the SMS-ICU¹⁴ focus of infection (other foci versus urinary tract infection)^{14,16} and use of corticosteroids¹⁷
 A two-tailed logistic regression analysis in the per-protocol population adjusted for the stratification variables

4. Two-tailed logistic regression analyses in the pre-planned subgroups adjusted for the stratification variables

We will report absolute and relative risk ratios with 95% CIs for the primary analysis of the primary outcome (analysis 1) (P-value <0.05), computed using glm-models with appropriate link functions and binomial error-distribution. Further, we will report the crude event rates in each group and a Kaplan-Meier survival curve for the crude data of the primary outcome.

Secondary outcomes

Dichotomous secondary outcomes will be analysed in the same way as the primary analysis for the primary outcome, i.e.:

• SAEs

Two-tailed logistic regression adjusted for the stratification variables in the ITT population

- SARs
 Two-tailed logistic regression adjusted for the stratification variables in the ITT population
- 1-year mortality

Two-tailed logistic regression adjusted for the stratification variables in the ITT population

A Kaplan-Meier survival curve will be reported for the crude data for secondary outcome 1-year mortality.

The remaining secondary outcomes are continuous measures which we expect to be skewed (nonnormally distributed), because of inflation of specific values such as zero for 'days alive outside hospital' for all patients who die while in the ICU. The outcome measures will be analysed as follows:

- Days alive at day 90 without life support
 Generalised linear model or nonparametric test stratified for site in the ITT population
- Days alive and out of hospital at day 90
 Generalised linear model or nonparametric test stratified for site in the ITT population
- HRQoL 1-year after randomisation⁸
 Generalised linear model or nonparametric test stratified for site in the ITT population
- Cognitive function 1-year after randomisation⁹

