Generalised linear model or nonparametric test stratified for site in the ITT population For the generalised linear model we will initially use Poisson distribution, alternatively negative binomial.¹⁸ If the assumptions for Poisson distribution or negative binomial distribution are not met, data will be analysed using the nonparametric Van Elteren test adjusted for site, but no other variables.¹⁹

The following secondary outcome measures are composite; SAEs, SARs, days alive at day 90 without life support. We will report each component of these outcomes in an appendix to the primary publication without P-values due to the lack of adjustment for multiple comparisons. We will report absolute and relative risk ratios with 99% CIs for dichotomous secondary outcomes. For continuous secondary outcomes we will report mean differences with 99% CIs if they are normally distributed and medians with 99% percentile-based bootstrapped CIs for non-normally distributed continuous secondary outcomes (P-value 0.01) due to the multiplicity of these. A detailed definition of the level of significance for the secondary outcomes is available in the supplement to the published statistical analysis plan. ¹

Sample size

Primary outcome

We plan to enrol 1554 (2 x 777) patients to be able to show a 15% relative risk-reduction (RRR) (7% absolute) in the restrictive group on the primary outcome from an estimated 45% 90-day mortality in the standard care group at type 1 and 2 error levels of 5% and 20% respectively, corresponding to a number needed to treat (NNT) of 14 or less. The anticipated relative risk reduction of mortality and the estimated mortality in the control group is based on data from previous RCTs and systematic reviews.^{20–24}

Trial sequential analysis of existing trials (n=8) have shown that less than 15% of the required information size of 3956 patients to detect or reject a 15% RRR in all-cause mortality with lower versus higher fluid volumes has been reached.²⁵

Secondary outcomes

We expect to have the following statistical power for the secondary outcomes based on 2 x 777 participants, a type 1 error level of 1% and a RRR of 15% in the fluid restriction group versus standard care group:

- 50% power for the number of participants with one or more SAEs (control event rate 25% ^{21,22})
- 10% power for the number of participants with one or more SARs (control event rate 5%^{21,22})

- 80% power for the mortality at 1-year (control event rate 55%^{21,22})

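### SMS-ICU, a pre-randomisation score built to predict 90-day mortality, is kept out of the primary model: valid, but it gives up about 1 to 4 points of power

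*SAP*

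**What the plan says.** The SAP (Statistical analyses, Primary outcome) lists four analyses of 90-day mortality. The primary one is a two-tailed logistic regression with two covariates: "site and hematologic malignancy /metastatic cancer) in the ITT population". SMS-ICU appears in the next one, under Sensitivity analyses: "A two-tailed logistic regression analysis adjusted for the stratification variables, the SMS-ICU", together with focus of infection and corticosteroid use. Protocol section 10.2 has the same structure. It counts a higher SMS score among the important baseline risk factors, but uses it to test the primary result and not to produce it.

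Protocol Appendix 6 gives the score as a table of predicted 90-day mortality, from 3.3% at score 0 to 91.0% at score 42. On timing it says: "In trial settings, the variables are measured in the 24-h period before randomisation". Appendix 2 agrees, and section 9.2.2 places the score items among the baseline variables. The SAP also names the score as an imputation variable.

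The sample size takes no credit for covariates: "We plan to enrol 1554 (2 x 777) patients", "from an estimated 45% 90-day mortality in the standard care group", "at type 1 and 2 error levels of 5% and 20% respectively". Under Missing data, the SAP prescribes complete cases when less than 5% of the data needed for an analysis are missing. Multiple imputation applies only above 5%, and only if the data are judged not missing completely at random. The SAP's summary of changes records that relative risks were obtained by G-computation from the logistic model, because the log- and identity-link models did not converge.

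**The concern.** A covariate that predicts the outcome and is fixed before randomisation sharpens the treatment comparison and corrects chance imbalance in severity. SMS-ICU targets the same endpoint at the same time point, its items are already to be collected, and a model containing it is already written. Calling the smaller model primary leaves that precision out of the result on which the trial's conclusion rests. The sample size has no allowance for dropout, so a few points of power are worth having. What is at stake is efficiency, not validity.

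**Working it through.** **Inputs from the documents.** Control mortality 45%; reduction 15% relative, rounded to 7 points (45% to 38%); exact 15% relative reduction 0.45 × 0.85 = 38.25%; two-sided 5% ("P-values will be two-tailed"); power 80%; 777 per arm.

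**Step 1. Reproduce the plan's figure.** Pooled two-proportion formula, with d = p1 − p2 and m the mean of the two proportions:

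n per arm = [1.960 √(2m(1−m)) + 0.842 √(p1(1−p1) + p2(1−p2))]² / d²

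- 45% vs 38%: [1.960 × 0.6968 + 0.842 × 0.6951]² / 0.07² = 777, total 1554. This matches exactly; power at 777 is 80.0%.
- 45% vs 38.25%: 836 per arm, total 1672; power at 777 is 77.1%.

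**Step 2. Add a prognostic covariate.** If it explains a share R² of outcome variance beyond what is already in the model, the effective sample size is 777/(1 − R²) per arm. The documents do not give R²; 2% to 10% is an assumption.

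| R² | Effective n per arm | Power, 45% vs 38% | Power, 45% vs 38.25% | Total N for 80% power, 45% vs 38% |
|---|---|---|---|---|
| 0 | 777 | 80.0% | 77.1% | 1554 |
| 2% | 793 | 80.8% | 77.9% | 1524 |
| 5% | 818 | 82.0% | 79.1% | 1478 |
| 8% | 845 | 83.2% | 80.4% | 1430 |
| 10% | 863 | 84.0% | 81.3% | 1400 |

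The saving runs from 1554 − 1524 = 30 to 1554 − 1400 = 154 patients.

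**Step 3. Check the range by simulation, isolating the gain beyond cancer.** A straight line through the Appendix 6 table on the log-odds scale has a slope of about 0.136 per point (0.137 was used). Scores were built from the Appendix 6 points with an assumed case mix:

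- age bands 5/20/55/20% (youngest to oldest);
- systolic pressure bands 7/35/48/10% (lowest to highest);
- acute surgery 25%, cancer 17%, respiratory support 50%, renal replacement therapy 8%;
- vasopressor for everyone, since it is an inclusion criterion.

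This gives mean 23 and SD 5.4. The table slope was multiplied by 0, 0.5, 0.75 or 1 with cancer kept at full strength. Each scenario had 4000 trials of 1554 patients. Site was not simulated.

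| Slope multiplier | Score AUC | Cancer only vs cancer + SMS-ICU (45% vs 38%) | Equivalent patients | Same, 45% vs 38.25% | Equivalent patients |
|---|---|---|---|---|---|
| 0 | 0.55 | 82.4% vs 82.4% | 0 | 77.8% vs 77.8% | 0 |
| 0.5 | 0.62 | 80.8% vs 81.5% | 37 | 78.1% vs 79.1% | 32 |
| 0.75 | 0.66 | 81.6% vs 83.2% | 77 | 78.3% vs 80.8% | 90 |
| 1 | 0.69 | 80.0% vs 83.5% | 149 | 78.9% vs 81.8% | 129 |

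Each simulated power has a standard error of about √(0.8 × 0.2/4000) = 0.6 points, so compare within rows, where both models were fitted to the same trials. The gain is 0.7 to 3.5 points whenever the score carries information, and nothing is lost when it carries none.

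**Step 4. Price the missing-data rule.** If 5% of participants were dropped for an incomplete score, effective n is 777 × 0.95/(1 − R²). For 45% vs 38%, power is 78.8% at R² = 2% (a net loss), 80.0% at 5% (no gain) and 82.1% at 10%.

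**The case against.** The strongest defence is that nothing here is an error. Adjusting for the stratification variables is valid, is supported by a cited methods paper, and uses covariates that are needed to randomise and so should be complete. The SMS-ICU model is pre-specified too; the only question is which model is called primary. The documents also give no figure for how well the score discriminates in septic shock. All of this stands. It limits the point to a modest efficiency gain, but does not remove it.

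A reader might infer four stronger things that the documents do not support.

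- *That the gain is 105 to 225 patients.* Taking the table at face value with a score SD of 4 to 6 gives R² of 0.064 to 0.127, and 1554 × R²/(1 − R²) gives roughly those numbers. But that compares with no adjustment at all, which is not the plan's primary analysis. Cancer (7 points) is already in the model and is worth an R² of 2% to 3% under assumed case mixes. Netting it out leaves about 56 to 190, and the top of that range needs both the widest SD and a table perfectly calibrated in this population. Vasopressor use (4 points) is the same for everyone.
- *That the change is free because the SAP already imputes missing scores.* Below 5% missing it does the opposite, as Step 4 shows.
- *That adjustment rescues a trial with 77% power.* The stated 7-point design reproduces 80.0%. The gap between 7 points and an exact 15% reduction is a separate rounding matter.
- *That the score is fully validated and cleanly defined.* The cited paper's title claims development and internal validation. The window is stated in three ways: at ICU admission (Protocol 9.2.2, lead line), 24 hours before randomisation (Appendices 2 and 6), and the first 24 hours in the ICU (Appendix 6 table note). Acute surgical admission is defined in Appendix 2 but not named in the 9.2.2 list.

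**Conclusion.** The point holds as a missed efficiency. The primary analysis is unbiased as planned, but it omits a baseline predictor of its own endpoint that the trial already intends to collect and model. The cost is about 1 to 4 points of power at 1554 patients, or roughly 30 to 150 patients. This rests on the assumed 2% to 10% of outcome variance explained beyond cancer, on the assumed case mix, and on no participant being lost for an incomplete score. The recommendation concerns the plan before unblinding. The SAP's summary of changes dates the final analyses to March 2022, so the point gives no ground for replacing the primary result afterwards. At that stage the SMS-ICU model stays a sensitivity analysis.

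**What to change.** Pre-specify before unblinding:

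1. Primary analysis: logistic regression with treatment, site, cancer and SMS-ICU as a continuous covariate.
2. Report the marginal risk difference and risk ratio by standardisation (G-computation). Adding a covariate changes the meaning of the conditional odds ratio, so the headline should stay on the marginal scale. This also avoids the log- and identity-link models that did not converge.
3. Keep the stratification-only model as a sensitivity analysis.
4. Amend the missing-data rule so that missing baseline SMS-ICU items are imputed even when under 5% are missing, and no randomised participant in the ITT population leaves the primary analysis for that reason.
5. Use one score window, the 24 hours before randomisation. Reconcile Protocol section 9.2.2 and the Appendix 6 table note with it, since a first-24-hours-in-ICU window could admit post-randomisation values. Name acute surgical admission in the baseline list.

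The cost is a few lines of SAP and protocol text, slightly more analysis work and imputation of some baseline items. No extra patients are needed.

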6.1 Experimental intervention

No IV fluids should be given unless one of the below extenuating circumstances occurs; in these cases, IV fluid may be given in measured amounts:

- In case of severe hypoperfusion or severe circulatory impairment defined by either:
 - Lactate 4 mmol/L or above
 - Mean arterial blood pressure below 50 mmHg (with or without vasopressor/inotrope)
 - Mottling beyond the kneecap (mottling score >2) OR
 - Urinary output less 0.1 mL/kg bodyweight/h, but only in the first 2 hrs after randomisation

A bolus of 250-500 ml of IV crystalloid solution may be given followed by re-evaluation. These criteria identify patients at increased risk of death [35, 36, 37], and were found feasible and not associated with harm in the CLASSIC pilot trial [5].

- In case of overt fluid losses (e.g. vomiting, large aspirates, diarrhoea, drain losses, bleeding or ascites tap) IV fluid may be given to correct for the loss, but not above the volume lost.
- In case the oral/enteral route for water or electrolyte solutions is contraindicated or has failed as judged by the clinical team, IV fluids may be given to:
 - Correct dehydration or electrolyte deficiencies.
 - Ensure a total fluid input of 1 L per 24 h (fluids with medications and nutrition counts as input).

IV fluids may be given as carrier for medication, but the volume should be reduced to the lowest possible volume for the given medication.

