6.5 Criteria for modification of interventions for a given trial participant

The clinical team may at any time violate the protocol if they find it to be in the best interest of the participant. We will have a CLASSIC trial hotline to enable discussion around the clock between the clinicians caring for trial participants and the CLASSIC trial team regarding protocol related issues.

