- Renal replacement therapy: Use of acute or chronic intermittent or continuous renal replacement therapy.

Definition of daily collected variables:

- -Fluid input and output in mL cumulated from the 24-h ICU charts
 - Total volume and specific type of IV isotonic crystalloids: isotonic saline and buffered solutions: Ringer's lactate, Ringer's acetate and PlasmaLyte™
 - o Total volume of other IV fluids: e.g. <10% glucose, glucose-potassium, sodium-potassium-chloride, half-saline
 - Total volume of albumin (4, 5 or 20% solutions combined)
 - o Total volume of fluids with medications: both parenteral and enteral
 - Total volume of fluids with enteral and parenteral nutrition: e.g. enteral nutrition solutions and >10% glucose, protein or lipid solutions given parenterally or enterally
 - o Total volume of non-nutritional enteral/oral fluids: e.g. water or soft drinks
 - o Total volume of blood products: defined in inclusion criteria
 - Urinary output on this day
 - o Any fluid volume removed during renal replacement therapy
 - Total volume of other losses on this day including drainage, aspirates, stools and bleeding

-Major protocol violation on this day:

The CLASSIC trial protocol Page 48/82

- \circ Restrictive group: IV fluids given without one of the extenuating circumstances occurring on this day (y/n)
- Standard care group: the violations (no IV fluid given) will be assessed from all the day form registrations regarding fluid input at the end of trial for each participant
- -Use of infusion of vasopressor or inotrope on this day: defined in the inclusion criteria
- Use of systemic corticosteroids on this day: defined in the baseline data
- -Use of mechanical ventilation on this day: invasive mechanical ventilation as the use of positive pressure ventilation using a ventilator via a cuffed tube (oral, nasal or tracheostomy). CPAP is NOT mechanical ventilation.
- -Use of renal replacement therapy on this day: any form of renal replacement therapy (e.g. dialysis, hemofiltration or hemo-diafiltration) at any rate on this day.
- -Plasma concentration of creatinine in µmol/L on this day

Definition of outcome measures

Primary outcome:

90 day mortality: death from any cause within 90 days post-randomisation.

Secondary outcomes:

- -Serious adverse events as at least one episode of either the following observed in the ICU:
 - Ischemic events defined as either
 - o Cerebral ischemia defined as any form of cerebral ischemia on a CT- OR MRI scan

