
Summary of changes to statistical analysis plan

Changes during conduct of the final statistical analyses in March 2022:

- The relative risks with 95% CIs of the primary outcome were computed by G-computation based on the logistic regression and not generalized linear models with log and identity links as the latter models did not converge.
- We specified that major protocol violations included both discontinuation or withdrawal from the trial protocol by patient, surrogate, clinician, or investigator AND violation of the IV fluid protocol. Patients having one of these violations were not included in the per-protocol population.
- We specified the planned subgroup of mechanical ventilation to include both invasive and non-invasive mechanical ventilation including continuous CPAP as this was the variable which had been collected in the baseline form throughout the trial period.

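### The per-protocol analysis excludes participants after randomisation under arm-specific rules but adjusts only for site and cancer, leaving selection bias of uncertain size and direction that the covariates of analysis 2 would partly address

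*SAP*

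**What the plan says.** The SAP (General analytical principles) states: "The per-protocol population is defined as the ITT population except those having one or more major protocol violations". It bases the trial's conclusion on the ITT analysis.

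Under Statistical analyses, Primary outcome, the primary model adjusts for the stratification variables. Analysis 2 is "A two-tailed logistic regression analysis adjusted for the stratification variables, the SMS-ICU¹⁴ focus of infection" and use of corticosteroids, with no restriction to the per-protocol set. Analysis 3 is "A two-tailed logistic regression analysis in the per-protocol population adjusted for the stratification variables". Protocol section 10.2 presents the risk-factor-adjusted and per-protocol analyses as separate challenges to the primary result and names no covariates for the latter.

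The violation rules are in Protocol Table 3 and Appendix 2:

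- **Restriction arm:** IV fluid on any ICU day without an extenuating circumstance.
- **Standard care:** "the violations (no IV fluid given) will be assessed from all the day form registrations" at the end of the trial, so a participant is excluded only for receiving none.
- **Either arm:** the SAP's summary of changes adds discontinuation or withdrawal by patient, surrogate, clinician or investigator, and says: "Patients having one of these violations were not included in the per-protocol population".

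Protocol section 6.5 says: "The clinical team may at any time violate the protocol" when they judge this best for the participant. Section 4.3.2 lets the intervention be stopped for intolerable events or in the participant's interest.

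**The concern.** Exclusion depends on what happens after randomisation, and the event that triggers it differs by arm. When a restriction participant is given fluid short of the permitted thresholds, that is a violation; when a standard-care participant is given the same fluid, that is compliance. Clinicians know the allocation and may depart from protocol on clinical judgement. The remaining groups may therefore differ in prognosis for reasons unrelated to the treatment effect.

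The plan adjusts for prognosis in analysis 2, where randomisation already balances it in expectation, and not in analysis 3, where exclusion can unbalance it. The per-protocol result could then appear to support or contradict the primary result through selection alone.

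**Working it through.** **1. Yardstick.** The documents give no violation rate and no mortality among violators, so there is no planned figure for this bias to reproduce. The scale comes from the sample size (Protocol 10.1.1): 45% against 38%, two-sided 5%, power 80%. With n = [1.960·√(2·0.415·0.585) + 0.842·√(0.45·0.55 + 0.38·0.62)]² / 0.07², n = (1.3657 + 0.5850)² / 0.0049 = 777 per arm, which matches the plan. The planned effect is thus about 7 points (6.75 if exactly 15% of 45%).

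**2. Restriction-arm exclusions, no true effect.** Let a share v of the restriction arm be excluded, with mortality m. Mortality in those left is (0.45 - v·m)/(1 - v). For v = 0.20 and m = 0.60, (0.45 - 0.12)/0.80 = 41.25%, a difference of -3.75 points. For m = 0.35, (0.45 - 0.07)/0.80 = 47.5%, or +2.5 points. Differences below are restriction minus standard care, in points; v and m are assumptions.

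| Excluded | m = 35% | m = 45% | m = 55% | m = 60% |
|---|---|---|---|---|
| 10% | +1.1 | 0 | -1.1 | -1.7 |
| 20% | +2.5 | 0 | -2.5 | -3.75 |
| 30% | +4.3 | 0 | -4.3 | -6.4 |

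**3. Standard-care exclusions.** The same formula with 3% of controls excluded for receiving no fluid (assumed) shifts the difference by -0.8 points if their mortality is 20% and by +1.1 if it is 80%.

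**4. What baseline adjustment recovers.** A null simulation of 1,000,000 participants had 45% mortality in both arms, a measured baseline severity S and an unmeasured later deterioration U. Assumed log-odds slopes per SD were 0.7 for mortality on S and on U, and 0.5 for violation where a driver is active. Risk differences were standardised from logistic models. Site and cancer were not simulated, so the model without S stands in for the planned one. With 20% of the restriction arm excluded:

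| What drives violation | Without S | With S |
|---|---|---|
| S only | -1.4 | 0.0 |
| S and U | -2.8 | -1.4 |
| U only | -1.5 | -1.4 |
| Neither, but early deaths have one third the chance of a violation | +2.4 | +2.2 |
| S and U, with the same early-death effect | -0.1 | +1.1 |

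Early deaths are assumed to be half of all deaths. For S and U without the early-death effect, 10% excluded gives -1.4 falling to -0.7, and 30% gives -4.1 falling to -2.1.

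The first row reaches zero by construction, because violation there depends only on the variable adjusted for. In the last row two opposing biases nearly cancel, and removing one exposes the other.

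**5. Sampling error.** With 20% excluded, 0.8 × 777 ≈ 622 remain against 777. The standard error of the difference is √(0.45·0.55·(1/622 + 1/777)) ≈ 2.7 points. A bias of 1.4 points is about half a standard error.

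**The case against.** **The direction.** A reader might infer that restriction participants are dropped because they are doing badly, so that the analysis leans towards restriction. The documents do not support this:

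- Protocol section 6.1 permits fluid "In case of severe hypoperfusion or severe circulatory impairment defined by either" of four listed criteria, and also for overt losses or a failed enteral route. Fluid for the protocol's own severe-deterioration criteria is not a violation. Worsening short of those thresholds can still prompt fluid that is, but section 6.5 speaks of best interest, not severity.
- One violation suffices, and the intervention runs for the whole ICU stay up to 90 days, so early deaths have less time to be excluded.
- A participant must survive and regain competence to withdraw in person. In Denmark (Appendix 5), failure to identify next of kin stops the intervention, while data from those who die before consent are kept. These routes select survivors. They exist in both arms, so they bias the contrast only if they bite unequally.

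This part of the objection stands in full.

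**The design.** Keeping the primary model and changing only the population is a coherent one-change-at-a-time choice, and extra covariates shift a conditional odds ratio through non-collapsibility. Neither defeats the change: the planned model can be shown alongside, and standardised risk differences and ratios do not have the non-collapsibility problem.

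**The covariates.** SMS-ICU covers the 24 hours before randomisation and contains no lactate. Its cancer item is already a stratification variable, and its vasopressor item is nearly constant because vasopressor or inotrope infusion is an entry criterion. Infection focus and corticosteroid use are not severity scores. So the gain is partial.

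**The stake.** This is a sensitivity analysis, and the conclusion rests on ITT. That limits the consequence but does not explain why prognostic adjustment is omitted here.

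**Conclusion.** The concern holds as an avoidable weakness in a sensitivity analysis. Arm-specific exclusion after randomisation removes the protection of randomisation, and the plan leaves out prognostic covariates it uses elsewhere. The bias favours restriction if excluded restriction participants are sicker than average. It can favour standard care if early deaths are less often excluded, or if withdrawals that select survivors fall more on the restriction arm.

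The range of +2.5 to -3.75 points rests on assumptions: no true effect, 45% mortality, 20% of the restriction arm excluded and violator mortality of 35% to 60%. Baseline adjustment removes the part carried by measured baseline severity. In the simulation that was about half when later deterioration also drove violation, and almost nothing when deterioration alone did. The ITT conclusion is unaffected.

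**What to change.** The SAP's summary of changes dates the final analyses to March 2022, so these are best added as labelled supplementary output:

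1. Fit analysis 3 with the covariates of analysis 2: stratification variables, SMS-ICU, focus of infection, and corticosteroid use specified as baseline use, since daily use is also recorded. Show the stratification-only model beside it, and report standardised risk differences and ratios from both.
2. Tabulate excluded participants by arm: number, reason, timing, SMS-ICU and 90-day mortality. This shows which way the selection runs.
3. State that baseline adjustment does not remove confounding by deterioration after randomisation, so agreement or disagreement with the ITT result should be read with that in mind.

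The cost is one extra model and one table. The variables are already in the planned data collection, and the primary analysis does not change.
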